1. PROTOCOL SUMMARY

1.1. Synopsis

Protocol Title: A Phase 1, Open-Label Study in Healthy Participants to Investigate the Pharmacokinetics of Ritlecitinib Following Single Oral Administration of Modified Release Formulations Under Fed and Fasted Conditions

Brief Title:

A Study to Learn How Different Manufactured Products of the Study Medicine Called Ritlecitinib are Taken up Into the Blood in Healthy Adults When Taken on an Empty Stomach or When Taken With a Meal in Healthy Adults.

Regulatory Agency Identification Number(s):

US IND Number: 130983

[EudraCT/EU CT] Number: 2023-505603-23-00.

ClinicalTrials.gov ID: N/A

Pediatric Investigational Plan Number: N/A

Protocol Number: B7981086

Phase: Phase 1

Rationale:

Ritlecitinib is a covalent and irreversible inhibitor of JAK3 with high selectivity over the other JAK isoforms (JAK1, JAK2, and TYK2). Ritlecitinib also inhibits irreversibly the TEC family kinases with selectivity over the broader human kinome. Treatment with ritlecitinib is expected to inhibit the inflammatory pathways mediated by IL-7, IL-15 and IL-21, all implicated in UC, CD, AA, RA, and vitiligo and therefore under development in these indications. Moreover, due to lack of activity against the other JAK isoforms, ritlecitinib is expected to spare immunoregulatory cytokines such as IL-10, IL-27 and IL-35, which are critical to the maintenance of immunosuppressive functions and immune homeostasis.

This study aims to investigate the PK and relative bioavailability of 2 new MR capsule formulations of ritlecitinib, MR1 (release duration: 6-8 hours) and MR2 (release duration:13-15 hours) as single doses in fasted and fed conditions.

Objectives and Endpoints

Objectives	Endpoints		
Primary:	Primary:		
To determine the PK profile and relative bioavailability of ritlecitinib as 2 MR capsule formulations, MR1 and MR2, relative to solution formulation under fasted conditions in healthy adult participants.	PK parameters of ritlecitinib (fasted): C _{max} , AUC _{inf} (if data permit), otherwise AUC _{last}		
Secondary:	Secondary:		
To evaluate the effect of food on ritlecitinib exposure following administration as 2 MR capsule formulations, MR1 and MR2 in healthy adult participants.	PK parameters of ritlecitinib (fed): C _{max} , AUC _{inf} (if data permit), otherwise AUC _{last} .		
To evaluate safety and tolerability of ritlecitinib following single oral administration as MR1 and MR2 capsule formulations in healthy adult participants.	Assessment of AEs, clinical laboratory tests, vital signs and 12-lead ECG.		

Overall Design

This is a single dose, open-label, randomized, 4-period, 6-sequence crossover study in a single cohort of approximately 12 healthy participants randomized to one of the sequences (containing 1 solution and 2 modified release [MR1 and MR2] capsule formulations of ritlecitinib) described in the table below where the treatment names A; B & C are representative. The first 3 periods are under fasted condition and the fourth period is under fed condition to investigate the effect of food on the PK of MR1 and MR2.

Study design and treatments				
Sequence	Period 1	Period 2	Period 3	Period 4
1 (n=2)	A	В	C	B, fed
2 (n=2)	В	C	A	B, fed
3 (n=2)	C	A	В	B, fed
4 (n=2)	A	В	С	C, fed
5 (n=2)	В	C	A	C, fed
6 (n=2)	С	A	В	C, fed

Treatment A: ritlecitinib 100 mg PO solution

Treatment B: ritlecitinib 100 mg (2×50 mg) MR1 capsules Treatment C: ritlecitinib 100 mg (2×50 mg) MR2 capsules

Number of Participants

A total of approximately 12 healthy male and/or female adult participants will be randomly assigned to study interventions in the study.

Study Population:

Key inclusion and exclusion criteria are listed below:

Inclusion Criteria

Participants must meet the following key inclusion criteria to be eligible for enrollment into the study:

- Participants aged 18 or older (or the minimal age of consent in accordance with location regulations) at screening.
- Male and female participants who are healthy as determined by medical evaluation including a detailed medical history, full physical examination (which includes BP and pulse rate measurement), clinical laboratory tests, and 12-lead ECG.
- BMI of 16 to 32 kg/m², and a total body weight >45 kg (99 lb).
- Participants who are willing and able to comply with all scheduled visits, treatment plan, laboratory tests, lifestyle considerations, and other study procedures.
- Capable of giving signed informed consent.

Exclusion Criteria

Participants with any of the following characteristics/conditions will be excluded:

- Evidence or history of clinically significant hematological, renal, endocrine, pulmonary, gastrointestinal, cardiovascular, hepatic, psychiatric, neurological, or allergic disease.
- Any condition possibly affecting drug absorption (eg, gastrectomy, cholecystectomy).
- Known immunodeficiency disorder, including positive serology for HIV, or a first degree relative with a hereditary immunodeficiency.
- Infection with hepatitis B or hepatitis C viruses according to protocol specific testing algorithm history.
- Participants with any of the specified acute or chronic infections or infection history.
- History of febrile illness within 5 days prior to the first dose of study intervention.

 PFIZER CONFIDENTIAL

- History of any lymphoproliferative disorder such as EBV related lymphoproliferative disorder, history of lymphoma, history of leukemia, or signs or symptoms suggestive of current lymphatic or lymphoid disease.
- Known present or a history of malignancy other than a successfully treated or excised nonmetastatic basal cell or squamous cell cancer of the skin or cervical carcinoma in situ.

Evidence of untreated or inadequately treated active or latent Mycobacterium TB infection.

Study Arms and Duration:

Study Interventions				
Intervention Name	ritlecitinib (100 mg) solution	ritlecitinib (100 mg) solution ritlecitinib (100 mg) MR1 r		
Use	Experimental			
Dose Formulation	PO solution	Capsule		
Unit Dose Strength	100 mg in 100 mL provided in dosing bottle	50 mg/capsule	50 mg/capsule	
Route of	Oral			
Administration				
IMP or NIMP/AxMP	IMP			

Study Interventions				
Study Interventions	Period 1	Period 2	Period 3	Period 4
Study Participants will receive a single dose of IP on Day 1 of each period. Interventions Description				

For a given participant, the total study duration from screening to follow-up phone call will be between approximately 8 to 11 weeks.

Screening will occur within 28 days prior to the first dose of the study intervention. Each participant will go through Periods 1 through 4 and dosing in each treatment period will be separated by at least 3 days to minimize any carryover effect.

Venous PK blood samples for PK analysis will be collected pre-dose and at times specified in the SoA.

Participants may be discharged between periods at the discretion of PI. Following final discharge, participants will receive a follow-up phone call 28 to 35 days following the last dose of study intervention.

Participants who discontinue prior to completion of the study for reasons unrelated to safety may be replaced at the discretion of the PI and the sponsor. Participants withdrawn for safety reasons will not be replaced.

Statistical Methods

This study will include relative bioavailability and food effect evaluations. In the relative bioavailability evaluation, natural log transformed AUC_{inf} (if data permit), AUC_{last}, and C_{max} of ritlecitinib will be analyzed using a mixed effect model with treatment, sequence, and period as fixed effects and participant within sequence as a random effect. In the food effect evaluation, dose-normalized natural log transformed AUC_{last} and C_{max} of ritlecitinib will be analyzed using a mixed effect model with treatment and sequence as fixed effects and participant within sequence as a random effect. For both the relative bioavailability and food effect evaluation, estimates of the adjusted mean differences (Test/Reference) and corresponding 90% confidence intervals will be obtained from the model. The adjusted mean differences and 90% confidence intervals for the differences will be exponentiated to provide estimates of the ratio of adjusted geometric means (Test/Reference) and 90% confidence intervals for the ratios.

The plasma concentrations of ritlecitinib will be listed and descriptively summarized by nominal PK sampling time, formulation and food condition. Ritlecitinib PK parameters will also be summarized by formulation and food condition. AEs, ECGs, BP, pulse rate and safety laboratory data will be reviewed and summarized on an ongoing basis during the study to evaluate the safety of participants. Any clinical laboratory, ECG, BP, and pulse rate abnormalities of potential clinical concern will be described. Safety data will be presented in tabular and/or graphical format and summarized descriptively, where appropriate.

Ethical Considerations:

The results of previous studies of ritlecitinib support the investigation of ritlecitinib for AA, RA, vitiligo, UC and CD. Taking into account the measures to minimize risk to participants, the potential risks associated with ritlecitinib are justified by the anticipated benefits of informing safety and pharmacokinetics of MR formulations of ritlecitinib for future clinical development of therapies localized to the gut.

This is a short-term PK study and therefore no benefit to the participants is expected.

Based on the current clinical and nonclinical experience with ritlecitinib and information from other JAK inhibitors and TEC family kinase inhibitors (eg, tofacitinib, ruxolitinib, baricitinib, upadacitinib, abrocitinib, ibrutinib and acalabrutinib), the important potential risks for ritlecitinib are: serious infections, opportunistic infections and viral reactivation, malignancy, and thromboembolism. Identified risks that could have adverse outcomes include: dermatologic effects (ie. rash, urticaria), decreased lymphocyte counts, and decreased platelet counts.

Participants will be expected to commit time and may experience some discomfort while undergoing study assessments. In addition, participants of childbearing potential must agree to use appropriate contraception methods. Participants should avoid vaccination with live attenuated replication-competent vaccines. It is recommended that participants keep their diet habits constant throughout the study.

1.2. Schema

Not applicable.

1.3. Schedule of Activities

The SoA table provides an overview of the protocol visits and procedures. Refer to the STUDY ASSESSMENTS AND PROCEDURES section of the protocol for detailed information on each procedure and assessment required for compliance with the protocol.

The investigator may schedule visits (unplanned visits) in addition to those listed in the SoA table, in order to conduct evaluations or assessments required to protect the well-being of the participant.

3 04:36	Visit Identifier Abbreviations used in this table may be found in Appendix 9: Abbreviations.	Screening									Trea	tment	Perio	d				Notes
On: 15-Nov-2023	Appendix 7. Appreviations.			Peri	od 1		Pe	riod 2		P	eriod	3		Period	14	Follow-up Contact	Early Termination/ Discontinuation	Follow-up contact will occur by telephone and must occur 28 to 35 days after the last administration of ritlecitinib.
pproved (Days Relative to Day 1	Day -28 to Day -2	Day -	Day 1	Day 2	Day 3	Day 1	Day 2	Day 3	Day 1	Day 2	Day 3	Day 1	Day 2	Day 3	28-35 Days after last dose in Period 4		
Appl	Study Day	-28 to -2	-1	1	2	3	4	5	6	7	8	9	10	11	12			
∂	Informed consent	X																
e19\Approve	CRU confinement		X	\rightarrow	\rightarrow	\uparrow	\uparrow	\rightarrow	\rightarrow	→	\rightarrow	\rightarrow	\rightarrow	\rightarrow	X			Period 4: final discharge from CRU. Participants may be discharged between periods at the discretion of PI.
e19f28ce	Inclusion/exclusion criteria	X	X															Inclusion/exclusion criteria should be updated on Day -1 since screening.

	Visit Identifier Abbreviations used in this table may be found in Appendix 9: Abbreviations.	Screening									Trea	tment	Perio	d				Notes
2023 04:36 (GMT)				Peri	od 1		Pe	riod 2		P	eriod	3		Period	14	Follow-up Contact	Early Termination/ Discontinuation	Follow-up contact will occur by telephone and must occur 28 to 35 days after the last administration of ritlecitinib.
3 04:36	Days Relative to Day 1	Day -28 to Day -2	Day -	Day 1	Day 2	Day 3	28-35 Days after last dose in Period 4											
2023	Study Day	-28 to -2	-1	1	2	3	4	5	6	7	8	9	10	11	12			
ed\Approved On: 15-Nov-	Medical/medication history (update)	X	X															Period 1 only. Include history of alcohol abuse, tobacco/nicotine containing products, licit and illicit drug use or dependence within 6 months of Screening. For Day - 1, records should be reviewed or updated only.

	Visit Identifier Abbreviations used in this table may be found in Appendix 9: Abbreviations.	Screening									Trea	tment	Perio	d				Notes
2023 04:36 (GMT)	Appendix 7. Appreviations.			Peri	od 1		Pe	riod 2		P	eriod	3		Period	14	Follow-up Contact	Early Termination/ Discontinuation	Follow-up contact will occur by telephone and must occur 28 to 35 days after the last administration of ritlecitinib.
3 04:36	Days Relative to Day 1	Day -28 to Day -2	Day -	Day 1	Day 2	Day 3	28-35 Days after last dose in Period 4											
202;	Study Day	-28 to -2	-1	1	2	3	4	5	6	7	8	9	10	11	12			
ce19\Approved\Approved On: 15-Nov-5	Physical examination	X	X			X			X			X			X		X	Complete (full) physical examination must either be conducted at Screening or upon Admission on Day -1 of Period 1 only; brief physical examination will be performed on Day 3 of each period or at early termination/discontin uation, and as needed per investigator discretion if there are findings during the previous examination, new/open adverse events.

	Visit Identifier Abbreviations used in this	Screening									Trea	tment	Perio	d				Notes
	table may be found in Appendix 9: Abbreviations .																	
2023 04:36 (GMT)				Peri	od 1		Pe	riod 2		P	eriod	3		Period	d 4	Follow-up Contact	Early Termination/ Discontinuation	Follow-up contact will occur by telephone and must occur 28 to 35 days after the last administration of ritlecitinib.
4:3	Days Relative to Day 1	Day -28 to		Day	Day 2	Day 3	Day	Day 2	Day 3	Day	Day 2	Day 3	Day	Day 2	Day 3	28-35 Days after last dose in Period		
30		Day -2	1	1	2	3	1	Z	3	1	Z	3	1	Z	3	4		
202	Study Day	-28 to -2	-1	1	2	3	4	5	6	7	8	9	10	11	12			
pproved\Approved On: 15-Nov-	Safety laboratory	X	X			X			X			X			X		X	• Participants should fast for at least 4 hours prior to any safety blood collection. Additional laboratory assessments may be performed if deemed necessary by the investigator. Refer to Table 5 in Section 10.2. Day 3 safety labs of every period to be done after PK blood sampling.
9\A	Demography, height and weight	X																

	Visit Identifier Abbreviations used in this table may be found in Appendix 9: Abbreviations.	Screening									Trea	tment	Perio	d					Notes
2023 04:36 (GMT)				Peri	iod 1		Pe	riod 2		P	eriod	3		Period	14	Follow-up Contact	Early Termination/ Discontinuation	•	Follow-up contact will occur by telephone and must occur 28 to 35 days after the last administration of ritlecitinib.
3 04:30	Days Relative to Day 1	Day -28 to Day -2	Day -	Day 1	Day 2	Day 3	28-35 Days after last dose in Period 4												
202,	Study Day	-28 to -2	-1	1	2	3	4	5	6	7	8	9	10	11	12				
On: 15-Nov-	Pregnancy test (WOCBP only)	X	X															•	Given that the participant will be confined in CRU for the entire study, if tested negative on admission, no further test is needed.
pproved\Approved	Contraception check	Х	X													X	X	•	The contraception check is to confirm that contraception, if applicable, is used consistently and correctly.
Srov	Review prior or concomitant treatments and medications	X	X	\rightarrow	X	X													
ce19\Apr	FSH (WONCBP only)	X																•	Serum FSH for confirmation of postmenopausal status only
$\tilde{\infty}$	Urine drug testing	X	X																
7e19f2	Supine 12-lead single ECG	X		X			X			X			X		X		X		Day 1 ECG to be done pre-dose.

Visit Identifier Abbreviations used in this table may be found in Appendix 9: Abbreviations.	Screening									Trea	itment	Perio	d				Notes
Days Relative to Day 1 Study Day			Peri	od 1		Pe	riod 2		P	eriod	3		Period	14	Follow-up Contact	Early Termination/ Discontinuation	Follow-up contact will occur by telephone and must occur 28 to 35 days after the last administration of ritlecitinib.
Days Relative to Day 1	Day -28 to Day -2	Day -	Day 1	Day 2	Day 3	28-35 Days after last dose in Period 4											
Study Day	-28 to -2	-1	1	2	3	4	5	6	7	8	9	10	11	12			
Supine blood pressure, pulse rate and temperature	X		X			X			X			X		X		Х	Day 1 vital signs are collected prior to pre- dose (baseline) blood drawn.
HIV, HBsAg, HBcAb, HCVAb QuantiFERON®TB Gold test or equivalent	X																If HBsAg is negative and HBcAb is positive, HBsAb should be evaluated.
QuantiFERON®TB Gold test or equivalent	X																
Study intervention administration Pharmacokinetic blood sampling			X			X			X			X					Please refer to Section 5.3.2 for details regarding dosing under fed and fasted state.
Pharmacokinetic blood sampling			X	X	X	X	X	X	X	X	X	X	X	X		Х	PK sample collection will be done pre-dose and at times post-dose as shown in Table 1 below.

	Visit Identifier Abbreviations used in this	Screening									Trea	tment	Perio	d				Notes
	table may be found in																	

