8.3.6. Pregnancy Testing

A urine or serum pregnancy test is required at screening. Following screening, pregnancy tests may be urine or serum tests, and must have a sensitivity of at least 25 mIU/mL. Pregnancy tests will be performed in WOCBP at the times listed in the SoA. Following a negative pregnancy test result at screening, appropriate contraception must be commenced, and a second negative pregnancy test result will be required at the baseline visit prior to starting the study intervention. Pregnancy tests will also be done whenever 1 menstrual cycle is missed during the active treatment period (or when potential pregnancy is otherwise suspected) and at the end of the study. Pregnancy tests may also be repeated if requested by IRBs/ECs or if required by local regulations. If a urine test cannot be confirmed as negative (eg, an ambiguous result), a serum pregnancy test is required. In such cases, the participant must be excluded if the serum pregnancy result is positive.

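### Section 8.3.6 requires an end-of-study pregnancy test that the Schedule of Activities does not schedule and waives on a confinement premise the protocol itself contradicts

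*Protocol*

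**What the plan says.** **Section 8.3.6 of the protocol** requires a pregnancy test at screening and a second negative result at baseline before dosing. It then adds tests for a missed menstrual cycle, and its list ends: "or when potential pregnancy is otherwise suspected) and at the end of the study". The same section leaves timing to the schedule: "Pregnancy tests will be performed in WOCBP at the times listed in the SoA".

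**The SoA (Section 1.3)** marks the pregnancy test at Screening and Day -1 only. The cells for Periods 1 to 4, the follow-up contact and early termination are empty. The note gives the reason: "Given that the participant will be confined in CRU for the entire study, if tested negative on admission, no further test is needed".

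**On confinement**, the SoA row for the clinical research unit says: "Period 4: final discharge from CRU. Participants may be discharged between periods at the discretion of PI". The Synopsis repeats the permission ("Participants may be discharged between periods at the discretion of PI"), and so does Section 4.1.

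**On follow-up**, the SoA says: "Follow-up contact will occur by telephone and must occur 28 to 35 days after the last administration of ritlecitinib".

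**On precedence**, the SoA introduces itself this way: "The SoA table provides an overview of the protocol visits and procedures". It then sends the reader to Section 8 for the details of each procedure.

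**The concern.** Both statements cannot be followed. A site working from the SoA would do two tests and stop, as the note tells it to. A site working from Section 8.3.6 would look for a third test and find no visit assigned to it.

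The reason given for the waiver does not hold either. Confinement for the whole study is the default layout of the schedule, but three places in the protocol let the investigator discharge participants between periods. Every participant who completes the study also leaves the unit well before the telephone contact.

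At stake is a safety check for a drug with fetal findings in animals (Section 4.2.1). A pregnancy too early to detect on Day -1, a possibility Section 10.4.2 recognises at inclusion, could show on a test at discharge. That would start the exposure-during-pregnancy reporting in Section 8.4.5.1. Without a scheduled test, detection depends on a missed cycle, a suspicion, or the participant's own report.

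**Working it through.** No sample size, power or error-rate figure is involved. The check sets the texts side by side and counts days.

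**Routine tests for each WOCBP**

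| Time | Section 8.3.6 | SoA row |
|---|---|---|
| Screening | required | scheduled |
| Baseline (Day -1) | required | scheduled |
| End of study | required | not scheduled; waived by the note |
| Total | 3 | 2 |

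An empty cell alone might be a table-reading artefact. The explicit waiver in the note shows that it is not.

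**Which text governs?** The SoA calls itself an overview and points to Section 8, while Section 8.3.6 points back to the SoA for times. Section 8.1 requires adherence to the design requirements and includes those in the SoA among them, but does not rank the SoA above Section 8. Appendix 2 (Table 6) ties laboratory tests to the SoA times. The conflict is not resolved by the text.

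**Day counts.** Inputs from the SoA: doses on Study Days 1, 4, 7 and 10; final discharge on Study Day 12 (Period 4 Day 3); telephone contact 28 to 35 days after the last dose. There is no Day 0, so Day -1 to Day 1 is 1 day.

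- Last scheduled test to last dose: 1 + 9 = 10 days.
- Last scheduled test to final discharge: 1 + 11 = 12 days.
- Last scheduled test to telephone contact: 10 + 28 = 38 days, up to 10 + 35 = 45 days.
- Final discharge to telephone contact: 28 − 2 = 26 days, up to 35 − 2 = 33 days. All of this is outside the unit, even with no discharge between periods.

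**Time outside the unit between periods.** Doses are at least 3 days apart (Section 4.1), and participants are observed for 48 hours after each dose (Section 6.1.1). The nominal gap is 72 − 48 = 24 hours. Three days is a minimum with no stated maximum, but no longer gap is planned.

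**What a discharge test would cover.** Study Day 12 is 2 days after the last dose. Of the 28 days of required contraception after that dose (Section 5.2, criterion 24), 28 − 2 = 26 days come after such a test.

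**The case against.** The strongest reply is that the sponsor's intent is clear and the error is only a leftover phrase. Section 8.3.6 defers to the SoA, and the SoA note is specific to this study and gives a reason. The wording about a missed cycle during treatment reads as generic where first and last dose are 9 days apart. On this view the phrase should simply be deleted. That is a legitimate repair, but it is still an amendment, and it leaves the note resting on a premise the protocol contradicts.

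A second reply concerns consequence, and most of it stands. A test after the fourth dose cannot keep a pregnant participant from being dosed. The elimination half-life is 1.1 to 2.5 hours (Section 2.2.4.1). Other safeguards remain: contraception checks at follow-up and early termination, testing for cause, the instruction to call if contraception stops (Section 5.3.1), and pregnancy exposure reporting. None of these schedules the test that Section 8.3.6 requires.

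Third, discharge between periods matters little on the nominal schedule. A test after a 24-hour gap could not show a conception from that gap. After MR2, stool is collected for up to 72 hours, which makes discharge impractical there. This also stands. A readmission test is useful mainly if a gap runs well past the minimum.

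Finally, a reader might infer from Section 4.4 that the test is due at the telephone contact and so cannot be done. The documents do not support that. Section 4.4 sets a trial-level closing date, for the last participant, and does not time an individual's test. Final discharge is a workable reading.

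**Conclusion.** The protocol is wrong as written. Section 8.3.6 requires a test that the SoA omits and expressly waives, and the ground for the waiver is contradicted in the Synopsis, the SoA and Section 4.1. The size is small: one of three routine tests is unscheduled, and the last scheduled test falls 10 days before the last dose and 12 days before final discharge. It should be corrected, as a minor safety and consistency error.

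A reader might go further and infer that sites will skip the test, or that pregnant women will be dosed because of the gap. Neither follows. Omission is possible but not certain, because the SoA refers to Section 8. The missing test bears on detecting and reporting exposure, not on preventing it. The PK analyses are not affected.

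The day counts assume the nominal schedule. The number of WOCBP among the approximately 12 participants is not stated, so the number of missing tests cannot be given.

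**What to change.** 1. Add a serum β-hCG test for WOCBP to the SoA at Period 4 Day 3 (final discharge) and at early termination. Serum is what Table 6, footnote d, specifies. Safety blood is already due at both visits; for discharge the SoA says: "Day 3 safety labs of every period to be done after PK blood sampling". No extra visit or needle is needed. Section 8.3.6 does not name early termination, so that test is a practical extension.
2. In Section 8.3.6, replace the end-of-study phrase with those named visits.
3. Reword the SoA note so that the waiver covers only WOCBP continuously confined from Day -1 to final discharge. After any discharge between periods, require a negative test before dosing on readmission.
4. State that the discharge test serves detection and reporting of exposure (Section 8.4.5.1). It does not cover the 28-day contraception window, for which the follow-up contraception check and for-cause testing remain.

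If the sponsor intends no end-of-study test, it should delete the phrase from Section 8.3.6 with a justification and still correct the confinement premise in the note.

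The cost is one added assay per WOCBP, a further test only for those discharged between periods, and a protocol amendment with the approvals that Section 10.1.1 requires.
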